### 4.3.4 Dose Finding Using a Modified Toxicity Probability Interval Design

The modified toxicity probability interval (mTPI) design [Ji Y, Li Y, Bekele BN 2007] with a target DLT rate of approximately 30% will be applied to identify the MTD in each of the studied dose combination sequences described above.

In each dose combination sequence separately, dose escalation and de-escalation decisions will be based on the mTPI design and will depend on the number of participants enrolled and number of DLTs observed at the current dose combination level. The number of DLTs will be based on the DLT evaluable population which consists of participants who finished Cycle 1. See Section 5.6 and Section 9.5.1 for details.

A minimum of 3 participants will be required at each dose combination level. However, depending on the accrual rate, 3, 4, 5, or 6 participants may be enrolled at each new dose combination level. In Table 2, the columns indicate the numbers of participants treated at the current dose combination level, and the rows indicate the numbers of participants experiencing DLT. The entries of the table are the dose-finding decisions: E, S, D, and DU represent escalating the dose, staying at the same dose, de-escalating the dose, and excluding the dose from the trial due to unacceptable toxicity, respectively. For example, if 0 out of

3 participants at a given dose combination level develop a DLT, then the dose can escalate to the next level. If 2 participants out of 3 develop a DLT, the dose will be de-escalated to the next lower dose level. If 3 out of 3 participants develop a DLT, this indicates an unacceptable toxicity at this dose combination. The dose combination should be de-escalated, and the current dose combination will not be explored further. If 1 out of 3 participants at a given dose combination level develops a DLT, then additional participants should be enrolled at that dose combination level following the rules below.

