When adding participants to a dose combination level in response to a “stay” decision, the number of additional participants to be enrolled is capped to minimize the exposure to a dose combination that may be unacceptably toxic (denoted as DU in [Table 2](#)). Secondly, to determine how many more participants can be enrolled at the dose combination level, one can count steps in diagonal direction (down and to the right) from the current cell to the first cell marked DU. For example, if 1 of 3 participants have experienced a DLT at a given dose combination level, no more than an additional 3 participants should be enrolled at this dose combination level until additional DLT data are available. This is because this dose combination level would be considered unacceptably toxic if all 3 of the additional participants experience a DLT (ie, 4/6 participants with DLT in [Table 2](#)). The same principles will be applied whether 3, 4, 5, or 6 participants are initially enrolled at that dose combination level.

A D or DU decision at the lowest dose combination level will stop the trial. An E decision at the highest dose combination level will result in staying at that level. During dose finding, it may be acceptable to deescalate to an intermediate dose combination that was not predefined and not previously-studied if evaluation of toxicity at such a dose combination is desired. If this approach is taken, 3 to 6 new participants may be enrolled at the new intermediate dose combination, and the rules should be used to determine further enrollment at this dose combination level.

Dose finding will end after 14 participants have been enrolled at any of the tested dose combinations, in each sequence separately, regardless of subsequent dose escalation decision.

The DLT rates across dose combination levels will be estimated under the assumption of a monotonic relationship between toxicity and dose in each column, in each row and along the main diagonal of the dose combination grid. In each dose combination sequence, the dose combination with an estimated DLT rate closest to 30% will be treated as a preliminary MTD. However, the totality of the data will be considered before deciding on the dose(s) to carry forward into the planned expansion phase, and the escalation schedule may be adjusted based on PK, pharmacodynamic, and safety data emerging throughout the trial.

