Note that although 30% was the target toxicity rate used to generate the guidelines in [Table 2](#), the observed rates of participants with DLTs at the MTD(s) may be slightly above or below 30%.

Dose escalation decisions will be made upon ongoing review of available PK, pharmacodynamic, and safety data at the current dose level.

Based on the emerging safety and/or efficacy signals, lower, intermediate or higher dose combination levels may also be explored in consultation and agreement with the investigators and Sponsor. The exact additional dose combinations in each sequence during dose escalation is not predetermined, which will allow for flexibility in dose escalation based on emerging safety data in the clinical trial. The protocol will be amended as necessary.

Table 2 Dose-finding Rules per mTPI Design

Number of participants with at least 1 DLT	Number of Participants Evaluable for DLT at Current Dose											
	3	4	5	6	7	8	9	10	11	12	13	14
0	E	E	E	E	E	E	E	E	E	E	E	E
1	S	S	S	E	E	E	E	E	E	E	E	E
2	D	S	S	S	S	S	S	S	E	E	E	E
3	DU	DU	D	S	S	S	S	S	S	S	S	S
4		DU	DU	DU	D	D	S	S	S	S	S	S
5			DU	DU	DU	DU	DU	D	S	S	S	S
6				DU	DU	DU	DU	DU	DU	D	S	S
7					DU	DU	DU	DU	DU	DU	DU	D
8						DU	DU	DU	DU	DU	DU	DU
9							DU	DU	DU	DU	DU	DU
10								DU	DU	DU	DU	DU
11									DU	DU	DU	DU
12										DU	DU	DU
13											DU	DU
14												DU

D = De-escalate to the next lower dose; DU = The current dose is unacceptably toxic; E = Escalate to the next higher dose; S = Stay at the current dose  
 Target toxicity rate = 30%.  
 Flat noninformative prior Beta (1,1) is used as a prior and  $\epsilon_1=\epsilon_2=0.03$  [Ji Y, Li Y, Bekele BN 2007], [Ji, Y. and Wang, S.-J. 2013]

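### The closest-to-30% rule for the preliminary MTD does not say that combinations coded DU are ineligible, nor what is declared when a sequence stops for toxicity at its lowest combination

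*Combined protocol and SAP*

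**What the plan says.** Section 4.3.4 gives the end-of-sequence rule: within each sequence, "the dose combination with an estimated DLT rate closest to 30% will be treated as a preliminary MTD". It names no candidate set, upper limit or tie rule. Sections 9.1 and 9.6.2 say only that DLT rates are estimated by isotonic regression. They do not say whether raw rates or posterior means go into it.

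On the dose-finding codes, Section 4.3.4 describes DU as "excluding the dose from the trial due to unacceptable toxicity" and says of the 3-of-3 example that "the current dose combination will not be explored further". The footnote to Table 2 has "DU = The current dose is unacceptably toxic" and, separately, "D = De-escalate to the next lower dose".

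On the lowest level, Section 4.3.4 stops the trial after D or DU there. Sections 1.2 and 4.1 say that if the diagonal escalation concludes at the starting dose, the study finishes with a single MTD. Table 1 lists DL1 as a possible diagonal MTD. None of these places separates a conclusion at DL1 because DL2 was too toxic from one because DL1 itself was.

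**The concern.** The preliminary MTD is the main product of each sequence and feeds the RP2D, the primary objective. A rule based on absolute distance from 30% treats over- and under-shooting alike, so a level well above target can beat a level with no DLTs. If DU levels compete, the rule can return a combination that the same section takes out of the trial.

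The diagonal MTD is also used inside this study, because Table 1 turns it directly into the off-diagonal starting combinations. With 0/14 at DL2 and 5/9 at DL3, naming DL3 instead of DL2 moves the Table 1 starts (MK-8353/selumetinib) from 100/25 mg and 50/50 mg to 150/50 mg and 100/75 mg.

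**Working it through.** **Inputs.** From the Table 2 footnote: "Target toxicity rate = 30"%, "Flat noninformative prior Beta (1,1) is used as a prior", and epsilon 0.03 on each side. From Section 4.3.4: dose finding ends once a combination has 14 participants, and enrolment after a stay decision is capped by counting diagonal steps to the first DU cell.

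**Table 2 reproduced.** With r DLTs in n participants the posterior is Beta(1+r, 1+n-r). The decision is the interval with the largest posterior mass per unit length among (0, 0.27), (0.27, 0.33) and (0.33, 1). DU replaces D when P(p > 0.30) exceeds 0.95. The 0.95 cut-off is not in the documents, but it reproduces all 114 cells; the other values tried between 0.90 and 0.97 miss 1 to 8 cells. For 5/9 the probability is 0.953 (DU). For 7/14 it is 0.950 to three decimals and the cell is D.

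**Two adjacent levels, raw rates.** Distance = |r/n - 0.30|. These are the DU results reachable through stay decisions under the cap:

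| DU result | Rate | Distance | Beats 0/n (distance 0.300)? |
|---|---|---|---|
| 5/9 | 0.556 | 0.256 | yes |
| 6/11 | 0.545 | 0.245 | yes |
| 7/13 | 0.538 | 0.238 | yes |
| 5/8 | 0.625 | 0.325 | no |
| 4/6 | 0.667 | 0.367 | no |
| 3/4 | 0.750 | 0.450 | no |
| 3/3 | 1.000 | 0.700 | no |

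One DLT at the lower level is enough to prevent it. Even 1/14 has distance |0.071 - 0.30| = 0.229, below 0.238. So above the lowest level, DU is selected only when the level below has zero DLTs.

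**A completed path.** At the upper level: 1/3 (S), 2/6 (S, at most 3 more), 5/9 (DU). The sequence returns to the level below, which fills to 0/14. The rates 0 and 0.556 are already ordered, so isotonic regression leaves them unchanged and the upper level is closest to 30%.

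**Posterior means instead.** The estimate is (r+1)/(n+2). Then 5/9 gives 6/11 = 0.545 (distance 0.245) and 0/14 gives 1/16 = 0.0625 (distance 0.2375), so the lower level wins. Only 7/13 against 0/14 still selects DU: 8/15 = 0.533, distance 0.233 against 0.2375. The answer therefore depends on an estimator that the plan does not name.

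**Lowest level.** After D or DU at the first combination tested, only that combination has data. It is closest to 30% whatever its rate, even at 3/3.

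**Frequency.** Simulation of the seven-level diagonal used 10,000 runs per setting, cohorts of 3 or 6, and isotonic regression on raw rates weighted by n. The true DLT curves are assumptions.

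| Assumed true DLT rates, DL1 to DL7 | DU selected, cohorts of 3 | DU selected, cohorts of 6 |
|---|---|---|
| .05 .10 .18 .25 .32 .40 .48 | 0.3% | 0.1% |
| .08 .15 .30 .40 .45 .55 .60 | 0.5% | 0.4% |
| .02 .03 .50 .60 .65 .70 .75 | 9.9% | 7.9% |
| .01 .02 .04 .50 .60 .65 .70 | 8.1% | 7.3% |
| .01 .02 .60 .70 .75 .80 .85 | 11.5% | 10.1% |
| .45 .55 .60 .65 .70 .75 .80 | 20.9% | 39.4% |

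A separate set of runs (6,000 per curve, cohorts of 3) gave 0.2-0.4% for gradual or moderate curves, and 4% and 10% for two steep ones.

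In the last row every DU selection comes from stopping at DL1. A D stop at DL1 that is then named MTD adds 42.2% (cohorts of 3) or 15.4% (cohorts of 6). Under that curve the question of what to declare at DL1 arises in 20.9 + 42.2 = 63.1% or 39.4 + 15.4 = 54.8% of trials.

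**The case against.** The best defence is that DU already means exclusion from the trial, and an excluded dose is not naturally a candidate for its MTD. Section 4.3.4 also expects observed rates at the MTD to lie only slightly off 30%, which 5/9 does not. This stands as the natural reading, and it reduces the defect to a missing link. It does not close the gap, because DU is defined among the dose-finding decisions, its stated consequence concerns further exploration, and the selection rule is a separate sentence with its own criterion.

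It can also be said that the MTD is only preliminary, that all available data are weighed before a dose goes to expansion, and that off-diagonal sequences start left of or below the diagonal MTD and are again run under mTPI. This limits the harm. But the weighing of all data is tied to the expansion dose, whereas Table 1 uses the diagonal MTD earlier.

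Three stronger readings are tempting, and the documents do not support them:

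- **D levels must be barred too.** D means only de-escalate. Dose finding ends at 14 participants whatever the next decision would be, so the plan does not let the last letter govern selection.
- **Beta(1,1) posterior means are required.** The plan names that prior for Table 2 and for the 80% credible interval, not for the isotonic estimate. Using it has its own cost. With 1/6 (E) below 5/14 (S), raw distances are 0.133 and 0.057 and pick 5/14. Posterior means give 2/8 = 0.25 and 6/16 = 0.375, distances 0.05 and 0.075, and pick a level from which Table 2 says to escalate.
- **Over-toxic selections are mostly due to this gap.** On an assumed curve that jumps from 8% to 50%, a combination with a true rate above 40% was selected in 40% of runs as written and still in about 36% with DU levels removed.

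Finally, 0/6 against 5/9 is not a valid example, because neither level has reached 14 and the sequence is not finished. The case that counts is 0/14 against 5/9, with the same distances.

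**Conclusion.** The point holds as an unresolved eligibility question in the MTD rule. It does not show that the plan intends to name an unacceptably toxic dose. Above the lowest level a DU selection needs zero DLTs one level down and raw rates (one exception with posterior means), so it is rare on gradual or moderate curves (about 0.1-0.5%) and appreciable on steep ones (about 4-12%). When the lowest combination is itself too toxic, the literal rule names it after a DU code in about 20-40% of trials, and Sections 1.2, 4.1 and 4.3.4 together do not say whether an MTD is then declared.

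These frequencies rest on assumed DLT curves and cohort sizes, the inferred 0.95 cut-off, re-entry allowed after D but not after DU, and an assumed tie rule (highest level if the tied estimate is below 30%, otherwise lowest). Only the diagonal was simulated, not the two-way grid. The 0/14-against-5/9 case and the DL1 case follow from the text without simulation.

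**What to change.** Reconcile Sections 1.2, 4.1 (with Table 1), 4.3.4 (with Table 2), 9.1 and 9.6.2 on three points:

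1. State that combinations coded DU are not eligible for selection as the preliminary MTD. In the worked case the selection then moves to the 0/14 level.
2. State what is declared when a sequence stops for D or DU at its lowest combination, and make the single-MTD statements for DL1 agree with it.
3. Name the point estimate that enters the isotonic regression (raw rate or posterior mean) and the tie rule. Pooling gives adjacent levels the same estimate, so ties are to be expected.

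Excluding D levels and adopting Beta(1,1) posterior means are design choices that the sponsor may consider; neither is needed to correct the text. The change takes a few sentences and no new data, and should be in place before any MTD is declared. Its cost is that occasionally a lower MTD, or none, is named.

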#### 4.4 Beginning and End of Study Definition

The overall study begins when the first participant signs the ICF. The overall study ends when the last participant completes the last study-related telephone-call or visit, withdraws from the study, or is lost to follow-up (ie, the participant is unable to be contacted by the investigator).

##### 4.4.1 Clinical Criteria for Early Study Termination

Recruitment in the study, or at (a) particular study site(s), may be stopped due to insufficient compliance with the protocol, GCP and/or other applicable regulatory requirements, procedure-related problems, or the number of discontinuations for administrative reasons is too high.

Early study termination will be the result of the following specified criteria:

1. Incidence or severity of adverse drug reactions in this or other studies suggest a potential health hazard to participants
2. Plans to modify or discontinue the development of the study drug
3. Quality or quantity of data recording is inaccurate or incomplete

Ample notification will be provided in the event of Sponsor decision to no longer supply MK-8353 or selumetinib.

## 5 STUDY POPULATION

Male/female participants at least 18 years of age with advanced/metastatic solid tumor(s) will be enrolled in the study.

Prospective approval of protocol deviations to recruitment and enrollment criteria, also known as protocol waivers or exemptions, is not permitted.

### 5.1 Inclusion Criteria

Participants are eligible to be included in the study only if all of the following criteria apply:

1. Have a histologically- or cytologically-documented, locally-advanced or metastatic solid tumor by pathology report and have received, or been intolerant to, all treatment known to confer clinical benefit.
2. Provide an archival or newly obtained tumor tissue sample and blood samples for assessment of RAS/RAF mutation and for biomarker analysis.
3. Have at least 1 measurable lesion as defined by RECIST 1.1 on imaging studies (computed tomography [CT] or magnetic resonance imaging [MRI]) as assessed by the investigator/local radiology review. Cutaneous lesions and other superficial lesions that are detectable only by physical examination and subcutaneous lesions detectable by CT are not considered measurable lesions for the purposes of this protocol, but may be considered as nontarget lesions.
4. Have a performance status of 0 or 1 on the Eastern Cooperative Oncology Group (ECOG) Performance Scale. (Obtain within 7 days prior to first dose of study treatment.)
5. Have the ability to swallow and retain oral medication.
6. Demonstrate adequate organ function as defined in [Table 3](#)

Note: All screening evaluations should be performed within the Screening period, and labs are to be obtained within 7 days of initiation of treatment.

Table 3 Adequate Organ Function Laboratory Values

System	Laboratory Value
Hematological	
Absolute neutrophil count	>1,500/mcL (>1,000/mcL)
Platelets	>100,000/mcL
Hemoglobin	>9 g/dL or >5.6 mmol/L a
Renal	
Serum creatinine or creatinine clearance (CrCl) (measured or calculated) b or Glomerular Filtration Rate (GFR) in place of CrCl	≤1.5 X ULN or ≥60 mL/min for participant with creatinine levels >1.5 X ULN
Hepatic	
Total bilirubin (serum)	≤1.5 X ULN or Direct bilirubin <ULN for participants with total bilirubin levels >1.5 X ULN
AST (SGOT) and ALT (SGPT)	<2.5 X ULN or ≤5 X ULN for participants with liver metastases
Coagulation	
International Normalized Ratio (INR) or Prothrombin Time (PT)	< 1.5 X ULN unless participant is receiving anticoagulant therapy
Activated Partial Thromboplastin Time (aPTT)	< 1.5 X ULN unless participant is receiving anticoagulant therapy
ALT (SGPT) = alanine aminotransferase (serum glutamic pyruvic transaminase); AST (SGOT) = aspartate aminotransferase (serum glutamic oxaloacetic transaminase); ULN = upper limit of normal a Criteria must be met without packed red blood cell (pRBC) transfusion within the prior 2 weeks. Participants can be on stable dose of erythropoietin (≥ approximately 3 months). b Creatinine clearance (CrCl) should be calculated per institutional standard. Note: This table includes eligibility-defining laboratory value requirements for treatment; laboratory value requirements should be adapted according to local regulations and guidelines.	

## Demographics

- Is Male or Female and a minimum of 18 years of age inclusive, at the time of signing the informed consent.

## Male Participants

- Must agree to use a contraception as detailed in Appendix 5 of this protocol during the treatment period and for at least 120 days after the last dose of study intervention and refrain from donating sperm during this period.

## Female Participants

9. Eligible to participate if she is not pregnant, not breastfeeding, and at least 1 of the following conditions applies:
  - a) Not a woman of childbearing potential (WOCBP) as defined in Appendix 5.

OR

  - b) A WOCBP who agrees to follow the contraceptive guidance in Appendix 5 during the treatment period and for at least 120 days, after the last dose of study intervention.

## Informed Consent

10. The participant (or legally acceptable representative if applicable) provides written informed consent/assent for the study. The participant may also provide consent/assent for future biomedical research. However, the participant may participate in the main study without participating in future biomedical research.

## 5.2 Exclusion Criteria

Participants are excluded from the study if any of the following criteria apply:

### Medical Conditions

1. Have had chemotherapy, definitive radiation, or biological cancer therapy within 4 weeks (2 weeks for palliative radiation) prior to the first dose of study treatment, or has not recovered to CTCAE Grade 1 or better from any AEs that were due to cancer therapeutics administered more than 4 weeks earlier (this includes participants with previous immunomodulatory therapy with residual immune-related AEs). Participants receiving ongoing replacement hormone therapy for endocrine immune-related AEs will not be excluded from participation in this study.
2. Have a history of a second malignancy, unless potentially curative treatment has been completed with no evidence of malignancy for 2 years.

Note: The time requirement does not apply to participants who underwent successful definitive resection of basal cell carcinoma of the skin, superficial bladder cancer or in situ cervical cancer, or other in-situ cancers.

3. Have clinically active central nervous system metastases and/or carcinomatous meningitis. Participants with previously-treated brain or meningeal metastases may participate and be eligible for treatment provided they are stable and asymptomatic (without evidence of progression by MRI scan of the brain separated by at least 4 weeks after treatment), have no evidence of new or enlarging brain metastases, are evaluated within 4 weeks prior to first study treatment administration, and are off immunosuppressive doses of systemic steroids at least 2 weeks prior to enrollment

4. Have an active infection requiring therapy.

Note: Rescreening is possible after the infection resolves.

5. Have known human immunodeficiency virus (HIV) and/or Hepatitis B or C infections, or known to be positive for Hepatitis B antigen (HBsAg)/ Hepatitis B virus (HBV) DNA or Hepatitis C Antibody or RNA. Active Hepatitis C is defined by a known positive Hep C Ab result and known quantitative hepatitis C virus RNA results greater than the lower limits of detection of the assay.

6. Have undergone major surgery and has not fully recovered from any effects of major surgery without significant detectable infection and/or toxicity.

Note: Surgeries that required general anesthesia must be completed at least 2 weeks before first study intervention administration.

Note: Surgery requiring regional/epidural anesthesia must be completed at least 72 hours before first study intervention administration and participants should be recovered.

7. Have clinically significant cardiovascular disease as defined by the following:

- a) Uncontrolled hypertension (at screening/baseline: systolic BP  $\geq$ 150 mmHg or diastolic BP  $\geq$ 95 mmHg, despite optimal therapy)
- b) LVEF  $<$ 55% measured by echocardiography (or multigated acquisition scan)
- c) Symptomatic heart failure (New York Heart Association grade II-IV), prior or current cardiomyopathy, or severe valvular heart disease
- d) Uncontrolled angina (Canadian Cardiovascular Society grade II-IV despite medical therapy)
- e) Clinically significant cardiac arrhythmia and/or conduction abnormality  $\leq$ 6 months prior to start of study treatment
- f) Myocardial infarction (MI) or acute coronary syndrome (ACS)  $\leq$ 6 months prior to start of study treatment
- g) Mean QTcF interval  $>$ 470 ms (based on mean of 3 measurements corrected for heart rate based on Fridericia's formula)

8. Have a history of thromboembolic or cerebrovascular events within 6 months prior to treatment start, including transient ischemic attacks (TIAs), cerebrovascular accidents (CVAs), deep vein thrombosis, or pulmonary embolism.

9. Have neuromuscular disorders associated with an elevated creatine kinase (eg, inflammatory myopathies, muscular dystrophy, amyotrophic lateral sclerosis, spinal muscular atrophy).
10. Have one or more of the following ophthalmological findings/conditions:
  - a) Intraocular pressure >21 mmHg, or uncontrolled glaucoma (irrespective of intraocular pressure)
  - b) Current or past history of central serous retinopathy or retinal vein occlusion
  - c) Retinal degenerative disease
11. Have a known history of Gilbert's Syndrome.
12. Have a history or current evidence of a gastrointestinal (GI) condition (eg, inflammatory bowel disease, Crohn's disease, ulcerative colitis) or impaired liver function or diseases that in the opinion of the investigator may significantly alter the absorption or metabolism of oral medications.
13. Have a known psychiatric or substance abuse disorder, or any other cognitive disorder per the opinion of the investigator, that would interfere with the participant's ability to cooperate with the requirements of the study.
14. Is pregnant or breastfeeding, or expecting to conceive or father children within the projected duration of the study, starting with the Screening Visit through 120 days after the last dose of study treatment.

